4.4 Safety Endpoints

The safety endpoints of this study are:

1. Frequency, severity and causal relationship of AEs, Serious Adverse Events (SAEs) and Adverse Events of Special Interest (AESIs) during the entire study period.
2. Antibody formation, evaluation pre-dose before each treatment, at four weeks after each treatment and at the final study visit.
3. Safety assessments by evaluating hematology, clinical chemistry, vital signs and ECGs as per study schedule.

Statistical Analysis Plan (SAP)

CROMA
est. 1976

5 SAMPLE SIZE AND POWER

The primary efficacy endpoint is a composite endpoint comprising investigator and subject assessments of treatment effectiveness using the FWS. Composite endpoint treatment success (CETS) is defined as ≥ 2 point reduction in FWS score at maximum frown achieving a score of 0 or 1 at the visit week 4 relative to baseline based on investigator assessment and subject assessment. Thus, a subject is a CETS “Responder” only if both investigator- and subject-rated success criteria are satisfied at the visit 4 weeks after baseline.

The primary analysis of efficacy is the proportion of responders in the BoNT/A-DP treatment group compared with the placebo treatment group. For superiority testing of BoNT/A-DP compared with placebo, the following assumptions for the sample size calculation will be used:

Item	Assumption	Comments
Underlying test	Fisher's Exact Test	Standard test for a response parameter for small numbers
Randomization scheme (BoNT/A-DP: Placebo)	3:1	More active treatment subjects to enlarge safety database
Power $1-\beta$	90%	Actual power is 92.3%
Significance level (α)	0.025 one-sided	
Response Arm BoNT/A-DP	46%	Conservative value based on the results of previous studies (BLESS I and BLESS II)
Response Arm Placebo	2%	Conservative value based on the results of previous studies (BLESS I and BLESS II)
Software		The sample size calculation was performed using the software nQuery Advisor [®] 8.2.1.0

Statistical Analysis Plan (SAP)

CROMA
est. 1976

Based on these assumptions, 39 subjects in the BoNT/A-DP arm and 13 subjects in the placebo arm are required, i.e., 52 subjects in total. This is a very small sample size and not sufficient for a detailed evaluation of the data, including subgroup analyses. Furthermore, the response rate could not be estimated with sufficient precision. Assuming a response rate of 46% in the BoNT/A-DP group, a two-sided confidence interval (CI) of 95% with a distance from the response rate to the CI limits of about 5.6% could be achieved with a sample size of 225 subjects in the BoNT/A-DP group. A 3:1 randomization of BoNT/A-DP (225 subjects) to placebo (75 subjects) is proposed, which is adequate for a precise estimate of response rate and for post-hoc sensitivity analyses (i.e., treatment-by-center and other subgroup analyses), also taking into account a drop-out rate.

In addition the sample size is justified in order to fulfill FDA request for additional subjects treated with BoNT/A-DP to provide an adequate Safety database.

In total, 353 evaluable subjects will be enrolled. Applying a 15% drop out rate will result in a total number of completing subjects of about 300.

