Based on these assumptions, 39 subjects in the BoNT/A-DP arm and 13 subjects in the placebo arm are required, i.e. 52 subjects in total. This is a very small sample size and not sufficient for a detailed evaluation of the data, including subgroup analyses. Furthermore, the response rate could not be estimated with sufficient precision. Assuming a response rate of 46% in the BoNT/A-DG group, a two-sided confidence interval (CI) of 95% with a distance from the response rate to the CI limits of about 5.6% could be achieved with a sample size of 225 subjects in the BoNT/A-DP group. We propose a 3:1 randomization of BoNT/A-DP (225 subjects) to placebo (75 subjects), which we believe is adequate for a precise estimate of response rate and for post-hoc sensitivity analyses (i.e. treatment-by-center and other subgroup analyses), also taking into account a drop-out rate.

In addition sample size is justified in order to fulfill FDA request for additional subjects treated with BoNT/A-DP to provide an adequate Safety database. In total, 353 subjects will be enrolled. Applying a 15% drop out rate would result in a total number of completing subjects of about 300.

Analysis Data Sets

Safety Analysis Set (SAF):

All subjects who received at least one injection with study medication (independent of whether it is BoNT/A-DP or placebo) will be valid for the SAF. Within the SAF a subject will be considered for the treatment actually received and not for the treatment assigned by randomization, if different. The SAF will be used for the evaluation of the safety assessments.

Full Analysis Set (FAS):

The FAS includes all randomized subjects. Within the FAS a subject will be considered for the treatment assigned by randomization and not for the treatment actually received, if different, i.e. following the intent-to-treat (ITT) principle. The FAS will be used for the evaluation of the efficacy assessments. The FAS serves as the primary efficacy analysis set.

Modified Full Analysis Set (MFAS):

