12. STATISTICS

12.1 Sample Size and Power Calculations

Primary Analysis:

The primary endpoint is a composite endpoint comprising investigator and subject assessments of treatment effectiveness using the FWS. Composite endpoint treatment success (CETS) is defined as ≥2 point reduction in FWS score at maximum frown achieving a score of 0 or 1 at the visit week 4 relative to baseline based on investigator assessment and subject assessment. Thus, a subject is a CETS "Responder" only if both investigator- and subject-rated success criteria are satisfied at the visit 4 weeks after baseline.

The primary analysis of efficacy is the proportion of responders in the BoNT/A-DP treatment group compared with the placebo treatment group. For superiority testing of BoNT/A-DP compared with placebo, the following assumptions for the sample size calculation will be used:

Item	Assumption	Comments
Underlying test	Fisher's Exact Test	Standard test for a response parameter for small numbers
Randomization scheme	3:1	More active treatment subjects to enlarge safety data base
Power 1-β	90%	Actual power is 92.3%.
Significance level (α)	0.025 one-sided	
Response Arm BoNT/A-DP	46%	Conservative value based on the results of previous studies (Bless I and Bless II)
Response Arm Placebo	2%	Conservative value based on the results of previous studies (Bless I and Bless II)
Software		The sample size calculation was performed using the software nQuery Advisor® 8.2.1.0.

Based on these assumptions, 39 subjects in the BoNT/A-DP arm and 13 subjects in the placebo arm are required, i.e. 52 subjects in total. This is a very small sample size and not sufficient for a detailed evaluation of the data, including subgroup analyses. Furthermore, the response rate could not be estimated with sufficient precision. Assuming a response rate of 60% in the BoNT/A-DG group, a two-sided CI of 95% with a distance from the response rate to the CI limits of about 5.6% could be achieved with a sample size of 225 subjects in the BoNT/A-DP group. We propose a 3:1 randomization of BoNT/A-DP (225 subjects) to placebo (75 subjects), which we believe is adequate for a precise estimate of response rate and for post-hoc

sensitivity analyses (i.e. treatment-by-center and other subgroup analyses), also taking into account a drop-out rate.

In addition sample size is justified in order to fulfill FDA request for additional subjects treated with BoNT/A-DP to provide an adequate Safety database.

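### Stated precision for the BoNT/A-DP response rate is too narrow: 225 subjects give a 95% CI half-width of about 6.5 percentage points at 46%, not about 5.6

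*SAP*

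**What the plan says.** The sample size sections first derive 39 + 13 = 52 subjects from Fisher's exact test (46% versus 2%, one-sided 0.025, stated actual power 92.3%). They then call this too small for detailed evaluation and for a sufficiently precise estimate of the response rate, and move to a larger active arm on grounds that include precision:

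- SAP section 5, for the active arm at 46%: the 95% interval would be one "with a distance from the response rate to the CI limits of about 5.6% could be achieved with a sample size of 225 subjects". It continues: "A 3:1 randomization of BoNT/A-DP (225 subjects) to placebo (75 subjects) is proposed".
- Protocol synopsis, Sample Size Calculation: the same 5.6% and 225, also at 46%.
- Protocol 12.1: the same 5.6% and 225, but introduced by "Assuming a response rate of 60% in the BoNT/A-DG group, a two-sided CI of 95" per cent. The power table in that same section uses 46%.

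On numbers enrolled, SAP section 5 adds "In total, 353 evaluable subjects will be enrolled" and "Applying a 15% drop out rate will result in a total number of completing subjects of about 300". It also cites subgroup and treatment-by-center analyses, drop-out, and an FDA request for more treated subjects in the safety database.

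**The concern.** A half-width of 5.6 points is too small for 225 subjects at a response rate near one half, where the binomial variance is close to its maximum. It is also odd that the same 5.6% is tied to the same 225 subjects at two different assumed rates.

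This matters because power needs only 52 subjects. The 5.6% is the one number offered for choosing 225 active subjects on precision; the other reasons carry no calculation. A reader who relies on it expects a tighter estimate of the active response rate than the design gives.

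**Working it through.** **Inputs.** Rate 46% (SAP 5, synopsis) or 60% (Protocol 12.1). Two-sided 95%, z = 1.96. Active arm 225, placebo 75, total 300. Enrolled 353, 3:1, 15% drop-out. SAP 8.6.2 plans Wilson intervals for the responder rates.

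**How the sample sizes connect.** 353 × 0.85 = 300.05, and 300.05 × 3/4 = 225.04, so 225 is the active arm after drop-out. The FAS contains all randomised subjects, so its expected active arm is 353 × 3/4 = 264.75, about 265.

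**Trying to reproduce 5.6% as stated.**

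Wald half-width = z × √(p(1 − p)/n) = 1.96 × √(0.46 × 0.54/225) = 1.96 × 0.03323 = 0.0651.

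Wilson half-width = z/(1 + z²/n) × √(p(1 − p)/n + z²/(4n²)) = 0.0646, with limits 39.6% and 52.5%.

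At 60%: 1.96 × √(0.60 × 0.40/225) = 0.0640 (Wald); Wilson 0.0635.

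The stated figure does not reproduce at either rate.

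**Half-widths in percentage points.**

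| n | Meaning | Rate | Wald | Wilson |
|---|---|---|---|---|
| 225 | active arm named in the sentence | 46% | 6.51 | 6.46 |
| 225 | same | 60% | 6.40 | 6.35 |
| 265 | active arm expected in the FAS | 46% | 6.00 | 5.96 |
| 265 | same | 60% | 5.90 | 5.86 |
| 300 | both arms together | 46% | 5.64 | 5.60 |
| 300 | same | 60% | 5.54 | 5.51 |

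**Other interval methods at n = 225 and 46%.** Continuity-corrected Wald 6.73, Agresti-Coull 6.46, Jeffreys 6.48, Clopper-Pearson 6.70. A 90% Wald interval gives 5.47. None is 5.6.

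**What would give 5.6.**
- At 46%: n = 1.96² × 0.46 × 0.54/0.056² ≈ 304 active subjects, or about 304/0.75 ≈ 405 randomised 3:1.
- At n = 225: p(1 − p) = 225 × (0.056/1.96)² = 0.1837, so a rate of about 24% or 76%.

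**The neighbouring figures do hold.** Exact Fisher power by enumeration for 39 versus 13 at 46% versus 2% is 92.27%, against 92.3% stated. 300/0.85 = 353.

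**The case against.** **The interval actually reported will rest on more than 225 subjects.** This stands. The primary set is the FAS, with missing assessments counted as non-response, so about 265 active subjects enter the calculation. The gap against the stated figure is then about 0.4 points (6.0 versus 5.6) rather than 0.9. It narrows the error but does not remove it, and the sentence ties 5.6% to 225 explicitly.

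**Nothing depends on the number.** This also stands. The plan sets no precision target and no decision rule. The 5.6% is an approximate description of what could be achieved, and precision sits beside subgroup and treatment-by-center analyses, drop-out and the safety database. A reader might infer that the trial misses a precision requirement or is too small. The documents do not support that.

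**The cause is unknown.** A reader might infer that the two-arm total of 300 was used by mistake for the active arm. At 46% the arithmetic fits (5.60 to 5.64), but no section says so, and two facts weaken the inference. First, at 60% the same substitution gives 5.51 to 5.54, nearer 5.5. Second, 225 subjects at about 75% to 76% also give about 5.6: 1.96 × √(0.75 × 0.25/225) = 5.66 points and 1.96 × √(0.76 × 0.24/225) = 5.58. A 75.0% rate does appear in Protocol 4.4.2.2, for investigator-assessed responders in BLESS II, though nothing links it to this calculation. A figure left unrevised when the assumed rate changed is also possible. The documents do not settle which explanation is right.

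**The 60% is a single leftover.** Fair. The power table in Protocol 12.1, the synopsis and the SAP all use 46%. It still needs aligning, and 60% does not rescue the 5.6%.

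**Conclusion.** The stated precision is wrong as written in all three places. With 225 BoNT/A-DP subjects the 95% half-width is about 6.5 points at 46%, roughly 16% wider than stated (6.5/5.6 = 1.16), and about 6.4 at 60%. On the expected FAS active arm it is about 6.0 at 46%.

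This rests on a single-proportion interval at the documents' own rates and on 3:1 allocation of 353 subjects. It is not sensitive to small changes in the assumed rate: at the BLESS I and BLESS II composite rates of 46.5% and 48.8% the Wald half-width with 225 subjects is 6.52 and 6.53. The conclusion does not depend on how 5.6% arose; n = 300 remains a possible but unconfirmed explanation.

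The consequence is limited to the precision part of the sample size justification. Power, the primary test, the analysis sets and the intervals to be reported are untouched.

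**What to change.** In SAP section 5, the protocol synopsis and Protocol 12.1, replace the precision statement with: *assuming 46%, the two-sided 95% CI half-width is about 6.5 percentage points with 225 BoNT/A-DP subjects (about 6.0 with the approximately 265 in the FAS)*. In Protocol 12.1, replace 60% by 46% so that it agrees with its own power table, the synopsis and the SAP.

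Do not change the sample size, and do not put an explanation of the old figure into the text unless the sponsor can confirm it from the original calculation. The cost is an edit in three places and a slightly less favourable precision figure.

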6 ANALYSIS POPULATIONS

6.1 Safety Analysis Set (SAF)

All subjects who received at least one injection with study medication (independent of whether it is BoNT/A-DP or placebo) will be valid for the SAF. Within the SAF, a subject will be considered for the treatment actually received and not for the treatment assigned by randomization, if different. The SAF will be used for the evaluation of the safety assessments and for the individual subject data listings.

6.2 Full Analysis Set (FAS)

The FAS includes all randomized subjects, regardless of whether they received study medication. Within the FAS, a subject will be considered for the treatment assigned by randomization and not for the treatment actually received, if different, i.e., following the intent-to-treat (ITT) principle. The FAS will be used for the evaluation of the efficacy assessments. The FAS serves as the primary efficacy analysis set.

6.3 Modified Full Analysis Set (MFAS)

The MFAS includes all randomized subjects who received at least one injection with study medication who had a baseline (visit 1 at day 0) and at least one post-dose in-clinic assessment with the FWS by either the investigator or the subject on visits at weeks 1, 2 or 4. Within the MFAS, a subject will be considered for the treatment assigned by randomization and not for the treatment actually received, if different, i.e., following the ITT principle. The MFAS will be used for the evaluation of the efficacy assessments.

6.4 Per-Protocol Analysis Set (PP)

The PP includes all randomized subjects who received at least one injection with study medication who had no significant protocol deviations and an in-clinic assessment with the FWS by the investigator and the subject at baseline (day 0) and at the week 4 visit. For the PP, all subjects will be assigned to the randomized treatment. The PP will only be analyzed for main efficacy outcome measures.

Statistical Analysis Plan (SAP)

CROMA
est. 1976

6.5 Protocol Deviations and Exclusions from Analysis Sets

Protocol deviations and exclusions of subjects from analysis sets will be identified at the Data Review Meeting (DRM) just prior to study unblinding for the IA.

Deviations from the protocol will be classified as major or minor.

The following protocol deviations are considered a priori to be major and will lead to exclusion from the PP population:

- Subject or investigator unblinded to treatment
- Improper storage of IMP and IMP temperature excursion without proper notice to the CRA
- Incorrect treatment allocation or dose
- Wrong injection points used

6.6 Data Review Meeting (DRM)

For the DRM appropriate listings displaying all relevant data will be provided to the Sponsor and serve as a source for the protocol deviations discussion about the classification into major and minor. No unblinding will be done for the creation of these listings.

The following protocol deviations will be assessed on a case-by-case basis and a final decision on a possible exclusion from the PP population will be done during the DRM:

- Inclusion/exclusion criteria violated
- Use of disallowed medications
- Serious breach of GCP
- Site staff performing the study assessment not trained
- Failure to discontinue subjects where appropriate

Subjects with minor protocol deviations will not be excluded from the PP population.

Unblinding will be done after the DRM has been conducted and the minutes have been signed.

Following the IA, the protocol deviations described above will be reviewed during the remainder of the study. In addition, the following protocol deviations will also be reviewed during the remainder of the study, however these will not impact on decisions made on the analysis populations:

- Subject re-treated despite not meeting all re-treatment eligibility criteria
- Photography not collected or available for all visits.

Statistical Analysis Plan (SAP)

CROMA
est. 1976

7 STATISTICAL CONSIDERATIONS AND ANALYSIS

7.1 Derived Variables

The below table provide the list of derived variables for various duration derivations and baseline derivations applicable for this study.

Variables	Formula
Derivation of Duration	
Study day at any visit	Date of interest – date of first dose of study drug, if date of interest is before date of first dose of study drug. Date of interest – date of first dose of study drug + 1, otherwise.
Extent of Exposure (Days)	Last exposure date – Date of first study medication administration + 1 where Last exposure date = Maximum of (last study medication administration date, last visit date, end of study date).
Extent of Exposure (Weeks)	Extent of exposure (days)/7
Baseline Derivations	
Baseline	The baseline value is defined as the last observation before treatment, i.e., pre-treatment values measured on the treatment day (baseline visit, day 0), and if missing or not evaluated, the value from screening visit.
Change from baseline	Post baseline value – Baseline value
Relative change from baseline	$[(\text{Post baseline value} - \text{Baseline value})/\text{Baseline value}] * 100$

7.2 Handling of Missing Data

7.2.1 Missing Data Analysis Methods

Analyses will be performed by visit. For responder analyses on visits at week 4 and week 12, missing in-clinic assessments (investigator or the subject) with the FWS at baseline or week 4 and week 12 visits will be assigned as being non-responders.

As sensitivity analyses, the following additional approaches for handling of missing values will be applied:

Statistical Analysis Plan (SAP)

CROMA
est. 1976

- Analysis on observed values only, i.e., missing values will be excluded from analysis.
- Last observation carried forward (LOCF).
- Tipping point analysis: each missing value will be assigned to either a response or non-response, so that all possible combinations of replacing one or more missing values within each treatment group will be analyzed. P-values will be calculated for each combination and graphically displayed using a scatter plot.

The analysis of the week 16 visit regarding the efficacy endpoint “percentage of responders at week 16 (after first treatment)” will be conducted on observed values only, i.e., missing investigator or the subject in-clinic assessments with the FWS at baseline or week 16 visit will be excluded from analysis but not assigned as being non-responders. Subjects who were re-treated before visit week 16 are considered to be non-responders. The same approach holds for the efficacy endpoint “percentage of responders at week 20 or later (after first treatment)” respectively. The analysis of the additional secondary efficacy endpoints “proportion of subjects with ≥ 1 point reduction in FWS score (at maximum frown) in the BoNT/A-DP and placebo groups during the first treatment cycle at week 16 and week 20 relative to baseline, based on both the investigators’ and the subjects’ in-clinic assessments” will be conducted in a similar manner on observed values only.

All analyses of the modified Skindex-16 (GL-QoL) Emotional and Social Functioning domains and overall scores will be conducted on observed values only, i.e., missing domain and overall scores will be excluded from analysis; no imputation of missing domain and overall scores will be performed. The same approach will be followed for the analyses of the FACE-Q scales.

The analysis of “responder” 4 weeks after re-treatment will be conducted on observed values only, i.e., subjects with missing investigator or the subject in-clinic assessments on FWS week 4 or at the preceding end of the cycle visit will be excluded from analysis.

7.2.2 Handling of Missing or Incomplete Dates

7.2.2.1 Imputation Rules for Missing or Partial AE Start Date:

If the cycle of onset is missing, the following rules will be applied.

If only Day of AE start date is missing:

If the AE start year and month are the same as that for the first dose date, then:

- If the full (or partial) AE end date is NOT before the first dose date or AE end date is missing, then impute the AE start day as the day of first dose date.
- Otherwise, impute the AE start day as 1.

Statistical Analysis Plan (SAP)

CROMA
est. 1976

Otherwise, if the AE start year and month are not the same as that for the first dose date, then impute the AE start day as 1.

Compare the imputed AE start date with the first dose date to determine whether the AE is pre-treatment AE or treatment emergent adverse event (TEAE).

If only Day and Month of AE start date are missing:

If AE start year = first dose year, then:

- If the full (or partial) AE end date is NOT before the first dose date or AE end date is missing, then impute the AE start Month and Day as the Month and Day of first dose date;
- Otherwise, impute the AE start Month as January and the AE start Day as 1.

Otherwise, if AE start year not equal first dose year, then impute the AE start Month as January and the AE start Day as 1.

Compare the imputed AE start date with the first dose date to determine whether the AE is pre-treatment AE or TEAE.

If Year of AE start date is missing:

If the year of AE start is missing or AE start date is completely missing then query site with no imputation. Also compare the full (or partial) AE end date to the first dose date. If the AE end date is before the first dose date then the AE should be considered as a pre-treatment AE. Otherwise, the AE will be considered as TEAE.

